5.1 Pre-Study Screening Tests and Safety Assessment

5.1.1 *Pre-Study Screening Tests*

Pre-study screening tests, which are also enrollment evaluations, must be performed according the following time frames:

Within 4 weeks: tumor assessments based on contrast CT of chest, abdomen, and pelvis, and optional blood and serum samples.

Within 2 weeks: medical history, physical exam, vital signs, height, weight, ECG, ECOG, evaluation of symptoms and medications, clinical chemistry, hematology, coagulation, and troponin I.

Within 1 week: pregnancy test for women of child-bearing potential.

5.1.2 *Safety Assessment*

The safety of CPI-613 will be assessed from the first dose to 1 month after last dose of CPI-613. The assessment will be based on:

- evaluation of symptoms
- vital signs
- ECOG performance status and survival
- clinical chemistry
- renal function
- hematology
- coagulation
- cardiac safety assessments via troponin I and ECG

The specifics of the safety tests are described in Section 5.2. All safety assessment tests are performed during screening (performed within 2 weeks prior to treatment with CPI-613 during Pre-Cycle 1), on Day 5 during Pre-Cycle 1, and prior to each treatment cycle with results available for review within 24 hrs before administration the anti-tumor agents. Chemistries, hematology, and renal function will also be performed on Days 1 and 4 of each treatment week during the first 2 cycles. ECOG performance status and survival will be assessed on Day 1 of each treatment week.

5.1.3 *Tumor Assessment*

Tumor response to treatment will assessed at baseline, and initially after the time frame encompassing the pre-cycle 1 treatment and the first three cycles using

Comprehensive Cancer Center of Wake Forest University
A Pilot Study: Open-Label Clinical Trial of CPI-613 in Patients with Advanced Bile Duct
Cancers
CCCWFU # 59212

contrast CT of the chest, abdomen and pelvis as well as serum levels of tumor marker CA-19-9 and performance status. Should the principal investigator determine that tumor progression has occurred the patient will be removed from the study. Should the principal investigator determine that the patient has stable disease or has had a favorable response, those patients will continue treatment with CPI-613 for an additional three cycles (approximately three months). At that time, patients will then undergo re-imaging contrast CT, CA-19-9 and performance status.

According to the Response Evaluation Criteria in Solid Tumors (RECIST), the efficacy of treatment for solid tumors is determined by the tumor size. RECIST criteria are the golden standard to evaluate the tumor. In this study RECIST criteria will be used to evaluate response. However, there is a *pseudoprogression* phenomenon described with the use of CPI-613 in Phase I solid tumor studies (Lee et al. 2012).

It is felt that if CPI-613-induces necrosis of the tumor lesion there may be some radiographic evidence for increasing size. CPI-613 induces tumor necrosis due to its mechanism of action – selectively targeting the altered form of mitochondrial energy metabolism in tumor cells, causing changes in mitochondrial enzyme activities and redox status, which leads to apoptosis, necrosis, and autophagy of tumor cells (2,3,7,17,18).

For the purposes of this study, pseudoprogression will be defined and considered in patients who meet RECIST criteria of progression. It will be the treating physician's discretion to continue treatment in this situation if the patient is deemed to be getting clinical palliative benefit. In these patients, the study drug can be given for another two cycles prior to making definitive determination of progression or response.

Assessment of tumor response will be the responsibility of the principal investigator and should be based on radiologic findings (i.e., contrast CT of the chest, abdomen, and pelvis, and MRI of the abdomen), CA-19-9 and performance status.

OS will be monitored bimonthly via telephone contact after treatment termination. (**Note:** During the bimonthly post-study telephone contact, information related to cancer treatment received after the study will also be collected). OS and PFS will be calculated from the first day of treatment. The duration of OS will be measured until the date of death or censored at follow-up. The duration of response (evaluated by PFS) will be measured from the date a first objective response is documented until the first sign of progression assessed by MRI and CT.

****NOTE:** Tumor necrosis alone should not be criteria for determining

Comprehensive Cancer Center of Wake Forest University
A Pilot Study: Open-Label Clinical Trial of CPI-613 in Patients with Advanced Bile Duct
Cancers
CCCWFU # 59212

progression.

Safety and RR of CPI-613 are the primary endpoints, whereas PFS and OS are secondary endpoints.

Pseudoprogession will be ruled out by allowing patients to receive the study drug for another 2 cycles after the first response assessment before making definitive assessment of progression or response. However, patients will not be allowed to continue treatment with CPI-613 at the time of “pseudo-progression” if any of the following criteria are met:

- a. The patient does not meet eligibility criteria set at the start of the protocol.
- b. Biliary function worsens.
- c. The patient has symptomatic progression.

OS will be determined from the first dose of CPI-613 to death, assessed up to 3 years after the first dose of CPI-613. Post-study survival, medical and cancer treatment information will be collected bimonthly via telephone contact after treatment termination.

RR is defined as % of patients who experienced a Complete Response (CR) or Partial Response (PR). CR and PR are based on Response Evaluation Criteria in Solid Tumor (RECIST) Version 1.1 Eisenhauer et al. 2009). The best response recorded from the start of the treatment until Disease Progression (DP) will be considered.

PFS will be determined from the first dose of CPI-613 to DP or death due to any cause, assessed up to 3 years after the first dose of CPI-613.

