2.2 Outcome Measures

The primary outcome measures are safety and anti-cancer activities (assessed based on Response Rate [RR]).

The secondary outcome measures are:

- Progression-Free-Survival (PFS).
- Overall Survival (OS).

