5.0 STUDY PROCEDURES

Table 5-1 (below) provides an overview of the study procedures for the pre-study screen and pre-cycle 1 treatment period. The specifics are described in subsequent sections.

Table 5-1: Study Procedures for Pre-Study Screen and Pre-Cycle 1 Treatment Period

Assessments	Pre-Study Screen ⁸	Pre-Cycle 1 treatment (Given Only Once for Each Patient)	
		Days 1-5	Days 6-7
CPI-613 ¹		√	
Medical history	√		
Pregnancy test for women of child-bearing potential	√		
Evaluation of symptoms and vital signs	√ ³	√ ⁴	
ECOG performance status and survival	√		
Clinical chemistry, hematology and coagulation ²	√	√ ⁵	
Cardiac: Troponin I	√	√ ⁵	
Cardiac: ECG	√	√ ⁵	
CT w/ contrast (chest/abdomen/pelvis)	√		
CA-19-9	√		
Plasma CPI-613 concentrations, possibly metabolite concentrations, and possibly other analyses ⁶		√ ⁷	
Optional blood and serum samples ⁹	√		
Adverse event evaluation		√	√

ECOG = Eastern Cooperative Oncology Group; hr = hour; min = minute.

¹ CPI-613 is given as a 2-hr IV infusion via a central venous catheter.

² Specific chemistries are listed in section 5.2.2. Renal function will be assessed utilizing the Cockcroft-Gault formula. Coagulation (PT/PTT) will only be assessed at screening.

³ Other than evaluation of symptoms and vital signs, height and weight, physical exam, and medications are also determined during pre-study medical screening.

⁴ Perform on Days 1 and 4 only.

⁵ Perform on Days 1 and 5 only.

⁶ Obtained according to the following schedule: pre-dose (~5 min before dosing), and at 0.5, 1, 1.5, 2, and 4 hrs post-dose of CPI-613.

⁷ Day 1 only

⁸ Pre-study screening tests, which are also enrollment evaluations, must be performed according the following time frames:

Within 4 weeks: tumor assessment (CT w/ contrast), CA-19-9

Within 2 weeks: medical history, physical exam, vital signs, height, weight, ECG, ECOG, evaluation of symptoms and medications, clinical chemistry, hematology, coagulation, and troponin

Within 1 week: pregnancy test for women of child-bearing potential, pre-study labs and ECG obtained before enrollment may be used for Day 1

⁹ Optional blood and serum samples are for possible testing of biomarkers, predictors of biological responses, toxicity, genotype vs. drug response relationship, etc.

Comprehensive Cancer Center of Wake Forest University
A Pilot Study: Open-Label Clinical Trial of CPI-613 in Patients with Advanced Bile Duct Cancers
CCCWFU # 59212

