Table 5-2 (below) provides an overview of the study procedures for all treatment cycles and the follow-up period. The specifics are described in subsequent sections.

Table 5-2: Study Procedures for All Treatment Cycles and Follow-Up Period

Assessments	Cycles 1 and 2 (Each cycle is 4 weeks)								Cycles 3 through 12 (Each cycle is 4 weeks)								Follow-Up Every 2 months until death
	Week 1		Week 2		Week 3		Week 4		Week 1		Week 2		Week 3		Week 4		
	D1	D4	D1	D4	D1	D4	D3,4,or 5		D1	D4	D1	D4	D1	D4	D3, 4, or 5		
CPI-613 ¹	√	√	√	√	√	√			√	√	√	√	√	√			
Evaluation of symptoms and vital signs	√ ²		√ ²		√ ²				√ ²		√ ²		√ ²				
ECOG performance status and survival	√ ²		√ ²		√ ²				√ ²		√ ²		√ ²				
Clinical chemistry, hematology ^{2,3,9}	√ ²	√	√	√	√	√			√ ²								
Cardiac: Troponin I and ECG ⁹	√ ²								√ ²								
CT w/ contrast (chest/abdomen/pelvis)																√ ⁴	
CA-19-9																√ ⁴	
Plasma CPI-613 concentrations, possibly metabolite concentrations, and possibly other analyses ⁶	√ ⁸																
Optional blood and serum samples ¹⁰																√ ⁴	
Phone contact																√ ⁷	

ECOG = Eastern Cooperative Oncology Group; hr = hour; min = minute; D1 = day 1; D4 = day 4.

¹ CPI-613 is given as a 2-hr IV infusion via a central venous catheter. Treatment with CPI-613 may be adjusted +/- 1 day.

² These tests are performed with results available for review within 24 hrs before administration of the anti-tumor agents.

³ Specific chemistries are listed in section 5.2.2. Renal function will be assessed utilizing the Cockcroft-Gault formula.

⁴ Performed at the following time points: during week 4 (preferably Wednesday or later) of cycle 3 for all patients. For patients without progression, perform during week 4 of cycles 6, 9, and 12. In patients where progression was detected from the cycle 3 scan, perform during week 4 of cycle 5. If patient remains on study after cycle 5, perform every 3 months thereafter.

⁶ Plasma samples will be obtained pre-dose (~5 min before dosing), and at 0.5, 1, 1.5, 2, and 4 hrs post-dose of CPI-613.

⁷ Survival and post-study cancer treatment will be monitored bimonthly via telephone contact after the patients are taken off the trial.

⁸ Cycle 1 only

⁹ Within 1 week: pre-study labs and ECG obtained before enrollment may be used for Day 1

¹⁰ Optional blood and serum samples are for possible testing of biomarkers, predictors of biological responses, toxicity, genotype vs. drug response relationship, etc.

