Appendix F - Post Study Bimonthly Telephone Follow Up Form

ORIS PID _____ Date of Bimonthly Telephone Call ____ / ____ / ____

Name of person completing form _____

What was the result of the telephone call?

- Call was unanswered
- Spoke directly with the subject
- Spoke to a family member
- Left a message

Comments:

Is this subject still living? Yes No Unknown

If the subject has expired, list date of death: ____ / ____ / ____

Is the subject currently receiving or has received since coming off the 59212 study systemic chemotherapeutic cancer treatment? Yes No

Type of cancer treatment being received (including the dose, dosing schedule and duration, if applicable and if known):

Is the subject receiving radiation for cancer treatment? Yes No

Type of radiation treatment being received:

ECOG Performance Status:

- 0 Fully active, able to carry on all pre-disease performance without restriction.
- 1 Restricted in physically strenuous activity but ambulatory and able to carry out work of a light or sedentary nature, e.g., light house work, office work.
- 2 Ambulatory and capable of all self-care but unable to carry out any work activities. Up and about more than 50% of waking hours.
- 3 Capable of only limited self-care. Confined to bed or chair more than 50% of waking hours.
- 4 Completely disabled. Cannot carry on any self-care. Totally confined to bed or chair.

COMMENTS: _____

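### Safety is to be assessed to 1 month after the last dose, but no dated contact with defined adverse-event collection falls in that month, and the coagulation schedule contradicts itself

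*Combined protocol and SAP*

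**What the plan says.** Section 2.2 names safety as a primary outcome alongside response rate. Section 5.1.2 gives the window: "The safety of CPI-613 will be assessed from the first dose to 1 month after last dose of CPI-613". It lists what the assessment rests on: symptoms, vital signs, performance status and survival, chemistry, renal function, hematology, coagulation, troponin I and ECG. It then says that all of these tests are done at screening, on Day 5 of Pre-Cycle 1, "and prior to each treatment cycle with results available for review within 24 hrs" of dosing.

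After treatment, the follow-up column of Table 5-2 reads "Every 2 months until death". Footnote 7 gives the purpose of the calls as survival and post-study cancer treatment; section 5.1.3 adds medical information without defining it. The call form, Appendix F, begins with "What was the result of the telephone call" and goes on to vital status, later chemotherapy, radiation, performance status and free comments. Section 6.3 asks the investigator to try to contact the patient and carry out a final evaluation when treatment is terminated.

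On coagulation, Table 5-1 footnote 2 says: "Coagulation (PT/PTT) will only be assessed at screening". The laboratory row of Table 5-2 is headed "Clinical chemistry, hematology" and does not mention coagulation.

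**The concern.** The plan commits to a safety window that its schedule does not fill. A patient who has stopped treatment has no next cycle, so the tests tied to the start of each cycle no longer occur. What remains is a call that comes too late and a form that does not ask about adverse events.

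An event that begins in that month would reach the database only if the patient or the treating team volunteered it, or if it happened to be known at the final evaluation. An event recalled at about 2 months is harder to date, grade and attribute. Section 9.0 reports toxicity by grade in 10 patients, so incomplete collection could leave those rates too low.

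The coagulation conflict is a separate matter. A site that follows the tables and a site that follows section 5.1.2 would collect different data for a listed part of the safety assessment.

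**Working it through.** The plan gives no figure for this point. The check compares the schedules and then counts days.

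**1. What falls in the month after the last dose**

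| Source | Content | Dated inside the month? | Collects adverse events? |
|---|---|---|---|
| Section 5.1.2 test schedule | Screening, Pre-Cycle 1 Day 5, before each cycle | No, once treatment has stopped | Not applicable |
| Table 5-2, Week 4 | CT, CA-19-9, optional samples, in scan cycles only | Yes | No |
| Table 5-2, follow-up | Call every 2 months | No | No; survival and later treatment |
| Section 5.1.3, calls | Adds undefined medical information | No | Not specified |
| Appendix F | Vital status, therapy, performance status, comments | Follows the calls | No field |
| Section 6.3 | Final evaluation, best effort | No date given | No content given |

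The row for adverse event evaluation in Table 5-1 covers Pre-Cycle 1. Table 5-2 has no such row for any cycle or for follow-up.

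**2. Timeline from the last dose**

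Section 6.0 gives doses on Days 1 and 4 of Weeks 1 to 3 of a 4-week cycle. The last dose of a full cycle is therefore cycle day 2 × 7 + 4 = 18. Assume 1 month = 30 days.

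- End of window: 18 + 30 = cycle day 48.
- Week 4 visit on Day 3, 4 or 5: cycle day 24, 25 or 26, which is 6 to 8 days after the last dose.
- Day 1 of a next cycle: cycle day 29, which is 11 days after the last dose. It does not occur in a patient who has stopped.
- First call: about 2 months after the patient goes off trial, if the 2-month interval runs from that date. This is after the window closes.

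**3. Share of the safety window**

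Day of last dose = 7 (Pre-Cycle 1 week) + 28 × (cycles − 1) + 18. Share = 30 / (day of last dose + 30).

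- 3 cycles: 7 + 56 + 18 = day 81; 30 / 111 = 27%.
- 12 cycles: 7 + 308 + 18 = day 333; 30 / 363 = 8%.

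**4. Effect on a reported rate**

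One patient with a missed event moves a rate in 10 patients by 1/10, or 10 percentage points. That holds for any omission at this sample size. The documents give no basis for estimating how many events would be missed.

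**5. Coagulation**

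| Source | Timing |
|---|---|
| Section 5.1.2 | Screening, Pre-Cycle 1 Day 5, before each cycle |
| Table 5-1, row | Grouped with chemistry and hematology, marked for screening and Days 1 and 5 |
| Table 5-1, footnote 2 | Screening only |
| Table 5-2 | Not listed |

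These cannot all be followed.

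**The case against.** The strongest reply is that the month is not empty. If treatment stops because of a Week 4 scan, the final evaluation in section 6.3 could well take place within days of the last dose. Section 6.2 requires patients with Grade 3 or 4 toxicity probably related to the drug to be monitored for recovery. Section 8.1 makes all Grade 3 to 5 events reportable whether listed or not, and the log in Appendix C has onset and stop dates with no cut-off.

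This stands in part. A reader might infer that there is no contact at all after the last dose; the documents do not support that. But the final evaluation has no date or content, the section 6.2 monitoring follows an event already known, and the reporting rules say what to do with an event once found. None of them schedules a search for new events in that month.

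A reader might also infer that toxicity rates will be biased downward, above all in patients who stopped for toxicity. The documents show no late-toxicity pattern, and the section 6.2 duty gives those patients some cover. Understatement is possible, not established.

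For coagulation, it is tempting to conclude that no on-treatment data would exist. That follows only if footnote 2 governs, and section 5.1.2 says otherwise. The effect on the planned toxicity table is also limited, because the list in section 8.1 has no coagulation term.

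Finally, dose-limiting toxicity is judged through the first cycle and the analyses are mainly descriptive. The gap therefore bears on the completeness of the safety description more than on the dose decisions.

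**Conclusion.** The point holds in a limited form. The plan sets a safety window to 1 month after the last dose for a primary outcome, and no dated contact with defined adverse-event collection covers that month. The uncovered part is about 27% of the window after Pre-Cycle 1 plus 3 cycles and about 8% after 12 cycles. These figures assume a 30-day month, dosing on schedule and a last dose on Week 3 Day 4. They are shares of time, not of risk. Toxicity rates in the 10 analysed patients could be understated, by an amount that the documents do not allow one to estimate.

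The coagulation issue is a contradiction between section 5.1.2 on one side and Table 5-1 footnote 2 and Table 5-2 on the other. It needs reconciling; the documents do not settle which schedule applies. Both points should be corrected, and neither invalidates the trial.

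**What to change.** 1. Schedule the first post-treatment call at 1 month after the last dose.
2. Add adverse-event fields to Appendix F: term, grade, start and stop dates, attribution.
3. Add an adverse-event row to Table 5-2 that covers the cycles and this call.
4. State in section 5.1.2 which of the listed assessments apply after the last dose. A call captures reported events but not laboratory or ECG findings, so the present list cannot be met by telephone alone.
5. Reconcile section 5.1.2 with Table 5-1 footnote 2 and Table 5-2 on coagulation.

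Items 1 and 2 cost one earlier call per patient and a form change. Items 3 and 5 are changes to the text. Item 4 adds no visit in itself, but if the sponsor keeps laboratory or ECG assessments in the post-treatment month, those would have to be scheduled and their cost accepted.

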CPI-613 is a novel anti-cancer agent (Zachar et al. 2011). CPI-613 selectively targets the altered form of mitochondrial energy metabolism in tumor cells, causing changes in mitochondrial enzyme activities and redox status which leads to apoptosis, necrosis and autophagy of tumor cells (Zachar et al. 2011). The activities of CPI-613 involve the catalytic and regulatory functions of the altered form of the pyruvate dehydrogenase complex (PDC) and the α -ketoglutarate dehydrogenase complex (KGDHC) found in tumor cells (Zachar et al. 2011). CPI-613 is also well-tolerated at doses up to 3,000 mg/m², according to Phase 1 trials in patients with solid tumors and hematologic malignancies. Although it has not been investigated in patients with cholangiocarcinoma, CPI-613 has exhibited anti-cancer activities against a variety of advanced cancers including different types of solid tumors (Lee et al. 2011 & 2012; Senzer et al. 2012) and hematologic malignancies (Pardee et al, 2011a and b, & 2012). Therefore, the anti-cancer activities and safety of CPI-613 against advanced bile duct cancers are investigated in this study. Interestingly, after the first two cycles of treatment, the radiologic response by CAT scan or PET scan did not correlate well with the clinical response for various tumor types, and patients had increased survival despite pseudo-progression on their initial scan. One of the reasons is that CPI-613 seems to be producing an inflammatory and necrotic local effect that can

Comprehensive Cancer Center of Wake Forest University
A Pilot Study: Open-Label Clinical Trial of CPI-613 in Patients with Advanced Bile Duct
Cancers
CCCWFU # 59212

be read as pseudo-progression on a standard CT. For this reason, we will allow patients to continue for an additional two cycles even if the first treatment scan shows progression of disease by RECIST criteria. After 2 additional cycles, we expect to understand if the patient responded to therapy or not as the inflammatory/necrotic effect should have subsided. Allowing 2 additional treatment cycles with Disease Progression according to RECIST cannot take place if any of the following conditions occur:

- the patient no longer meets eligibility criteria set at the start of the protocol (see Section 3.)
- worsening of biliary function when compared to baseline
- the patient has symptomatic progression

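### For patients continued after a first-scan RECIST progression, the plan does not date progression or reconcile the deferred call with the response window, and Appendix D does not match the section 9.0 response table

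*Combined protocol and SAP*

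**What the plan says.** Response rate (RR) is a primary outcome and PFS a secondary one (section 2.2). Section 5.1.3 defines both by disease progression (DP). For PFS: "PFS will be determined from the first dose of CPI-613 to DP or death due to any cause". For RR, with CR and PR taken from RECIST 1.1: "The best response recorded from the start of the treatment until Disease Progression (DP) will be considered".

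The same section makes an exception for suspected pseudo-progression. It applies to patients who already have RECIST progression: "pseudoprogression will be defined and considered in patients who meet RECIST criteria of progression". They may continue, and the call is postponed: "In these patients, the study drug can be given for another two cycles prior to making definitive determination of progression or response". Further on, pseudo-progression is to be ruled out by giving "another 2 cycles after the first response assessment before making definitive assessment of progression or response". Section 1 describes the same two cycles as treatment in the presence of RECIST progression: "Allowing 2 additional treatment cycles with Disease Progression according to RECIST cannot take place if any of the following conditions occur". Table 5-2, footnote 4, also treats the cycle-3 finding as progression and puts the rescan in week 4 of cycle 5.

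Other places differ. An earlier paragraph of section 5.1.3 takes a patient off study once the principal investigator finds progression. Section 6.3 speaks of progression confirmed after one additional cycle, whereas Appendix E says two.

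Section 9.0 plans Kaplan-Meier curves, 6-month and 1-year PFS rates, a table of CR, PR, SD and PD, and RR with a 95% interval. It gives no rule for dating progression. Appendix D codes each CT as stable disease, mixed response, pseudo-progression (first CT only), partial response or progression. Beside these stand the CT date and a yes/no item on whether the principal investigator judges the subject to have progressed.

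**The concern.** A patient can have RECIST progression at cycle 3 and a definitive call at cycle 5, and both endpoints end at DP without a statement of which scan sets its date. Two analysts following the text could date one confirmed progression eight weeks apart. They could also disagree on whether a cycle-5 response belongs in RR: the deferral suggests that it does, but a strict RECIST 1.1 window would already have closed.

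The plan expects this situation. It gives these patients their own rationale, scan schedule and form code. The study is open-label, continuation is at the treating physician's discretion, and the principal investigator assesses response. An unstated rule could therefore be settled after the scans are known, in an analytic sample of 10.

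The form adds a separate problem: its codes are not the categories that section 9.0 will tabulate.

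**Working it through.** **The plan's own figure.** Section 9.0 says that the 95% interval for RR reaches at most 0.31 from the estimate. With a normal approximation at p = 0.5 and n = 10, 1.96 × √(0.25/10) = 0.3099, so 0.31 reproduces. It describes sampling error only and does not bear on how a response is counted.

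**Scan days.** Inputs: a 7-day pre-Cycle 1 period and 28-day cycles (section 6.0), and scans on day 3, 4 or 5 of week 4 (Table 5-2). Day 1 is the first pre-Cycle 1 dose, and no dose delay is assumed. Study day for cycle c = 7 + 28(c − 1) + 21 + (3 to 5).
- Cycle 3: 7 + 56 + 21 + (3 to 5) = day 87–89.
- Cycle 4: 7 + 84 + 21 + (3 to 5) = day 115–117. No scan is scheduled here, although section 6.3 implies confirmation at about this time.
- Cycle 5: 7 + 112 + 21 + (3 to 5) = day 143–145.
- Gap between cycles 3 and 5: 143 − 87 = 56 days, or 8 weeks.

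**Progression confirmed at cycle 5.** Six months is 182.6 days, about day 183. Both candidate dates fall earlier, so the 6-month and 1-year PFS rates are the same under either reading. Between the two dates the curve is 1/10 = 10 points higher per such patient under cycle-5 dating, if there is no earlier censoring. The 6-month rate becomes sensitive only if accumulated delay reaches 183 − 145 = 38 to 183 − 143 = 40 days; section 6.2 allows dosing to be withheld.

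**Not called progressed at cycle 5.** Under deferral the event moves to a later progression or to death, whichever comes first, so the gap is not fixed. The next scan, three months on, falls at day 234–236 if that means 91 days, or at day 227–229 if it means three cycles (84 days). Both are after day 183. If the patient is alive and progression-free at day 183, 6-month PFS differs by 10 points between readings.

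**Response after a first RECIST progression.** Each such patient moves RR by 1/10 = 10 points. Exact (Clopper-Pearson) 95% limits, assumed here because section 9.0 names no method, are:
- 0/10: 0 to 30.8%
- 1/10: 0.3 to 44.5%
- 2/10: 2.5 to 55.6%

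**Does any wording settle the date?**
- The deferral says when the call is made, not which date the event then takes.
- One sentence ends at the first sign: "until the first sign of progression assessed by MRI and CT". But its clock starts elsewhere: "The duration of response (evaluated by PFS) will be measured from the date a first objective response is documented". It defines duration of response, so it cannot date PFS in a patient whose first scan shows progression.

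**Form against table.** PR, SD and PD are on Appendix D. CR is not. Mixed response and pseudo-progression have no stated mapping to the four categories. The form does not say how to answer the progression item when pseudo-progression is ticked, and it has no field for the date of progression.

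**The case against.** The strongest reply is that the plan largely answers the response question. Section 5.1.3 twice postpones the call on response as well as progression. Section 1 expects the two extra cycles to show whether the patient responded. Appendix D codes pseudo-progression separately from progression. A plan that waits until cycle 5 presumably means to use what it sees there. This stands. A reader might infer that the plan has no rule at all and that RR is equally open both ways, but the text does not support that. What remains is that the deferral is never squared with the RECIST 1.1 window ending at DP, and that the date of a confirmed progression is not given.

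Four further replies also stand:
- A reader might infer that the dating choice distorts the reported PFS rates. For confirmed progressors scanned on schedule it does not alter the 6-month or 1-year rate, the only PFS rates named in section 9.0.
- A reader might infer that first RECIST progression must be the headline date because RECIST 1.1 is named. The documents do not require this, and it would set aside a deferral written specifically for this drug.
- Section 6.3 governs length of treatment, so its one-cycle wording is not a further rule for dating PFS.
- Nothing makes Appendix D the sole source for the response table. The form has a comments field and no lesion measurements, so a claim that complete responses will be recorded as partial is conjecture.

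The analysis is also descriptive, and three conditions in sections 1 and 5.1.3 bar continuation.

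**Conclusion.** The point holds in a limited form and should be fixed. The plan leans towards a cycle-5 determination but does not date a progression confirmed there or reconcile the deferral with its response window.

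For a confirmed progressor the choice is worth 56 days of PFS, visible only in the curve before 6 months. For a patient not called progressed at cycle 5 it can be worth 10 points of 6-month PFS, and for each response after a first RECIST progression 10 points of RR.

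These sizes assume 10 analysed patients, the pre-Cycle 1 week given, no dose delay and no earlier censoring. The documents give no rate of continuation after a first-scan progression, so the number affected could be anywhere from 0 to 10 and the effects are illustrative. No type I error or power is at issue.

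Appendix D's missing complete-response option and its two unmapped codes are clear on its face. So are the contradictions over removal at progression and over one or two additional cycles.

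**What to change.** 1. In sections 5.1.3 and 9.0, before scans are read, state one rule for continued patients: which scan dates DP, and when the response window closes. Either reading is acceptable once stated. Report PFS and RR under the other reading alongside.
2. In Appendix D, add a complete-response option, require a RECIST 1.1 category at every scan even when mixed response or pseudo-progression is ticked, and record the date of first RECIST progression. If a not-evaluable category is added, add it to the section 9.0 table too.
3. Reconcile the removal-at-progression paragraph of section 5.1.3 with section 1 and the pseudo-progression text of 5.1.3. Reconcile the one additional cycle in section 6.3 with the two in section 1, section 5.1.3 and Appendix E. No clinical rule is proposed here.

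Removing the parenthesis that equates duration of response with PFS is an editorial tidy-up only; duration of response is neither an outcome in section 2.2 nor analysed in section 9.0.

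The cost is wording in a few sections and a small form edit, with no new scans. If patients are already enrolled, completed forms must be back-filled from scan reports. The second set of estimates may be less favourable than the first.
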